### Recruitment and Informed Consent

A random sample of SLE patients already recruited into the population-based GOAL study will be offered the opportunity to participate in the WELL Sub-study. Target enrollment will be 150 African American women who are resident of one of the metropolitan Atlanta counties where community-based CDSMP classes are provided. [Enrollment number increased to 168 to accommodate participants on a waiting list due to workshop cancellations and participants' rescheduling needs (e.g., illness, hospitalizations, and family emergencies)]. Each woman will have the same probability of being chosen at any stage of the sampling process. Thus, we will ensure

Table 1. Summary of Study Measures		
Category	Measure	Tool
Self-management Behaviors	Communication with Physicians	3-item scale
	Medication Adherence	MMAS-8
Health-related Quality of Life	Global Health	PROMIS
	Physical Function	PROMIS
	Pain Interference	PROMIS
	Fatigue	PROMIS
	Sleep	PROMIS
	Anxiety	PROMIS
	Social Function	PROMIS
Disease Severity	Disease Activity	SLAQ
	Organ Damage	SA-BILD
	Multimorbidity	CCHP
	Depression	PROMIS
Demographics	Age	Ad-hoc
	Education	Ad-hoc
	Employment	Ad-hoc
	Social Support	Ad-hoc
Health Service Utilization	ED visits	GA HDDB
	Hospitalizations	GA HDDB

MMAS: Morisky Medication Adherence Scale; PROMIS: Patient-Reported Outcome Measurement Information System; SLAQ: Systemic Lupus Activity Questionnaire; SA-BILD: Self-administered Brief Index Lupus Damage; ED: emergency department; GA HDDB: Georgia Hospital Discharge Database

representation of the AA female population in the CDSMP. The only exclusion criteria will be participation in the CDSMP in the past 5 years.

Women randomly selected will be mailed a flyer about the study and will receive a phone call by the Project Coordinator (PC) within the following week. During the phone call, the PC will assess the entry and exclusion criteria and will explain the study and level of participants' commitment needed to ensure study integrity. Interested participants will receive a packet with the consent, information of the CDSMP workshops schedule and location, a list of measures and study staff contact information. The PC will follow up with a phone call within 1 week to answer any questions and finalize the recruitment and CDSMP registration. Since this study entails minimal risk, interested GOAL participants will be consented via mail, e-mail, in person or telephone.

The PC will coordinate CDSMP schedules and locations with CDSMP leaders, in order to facilitate the registration of WELL participants in CDSMP workshops at convenient locations and schedules. Participants of the WELL Substudy will receive monetary compensation for the research tasks (gift cards of \$35 \$40, \$45 and \$50 for the baseline, 6-, 12- and 18-month assessments, respectively, and a round-trip MARTA card, \$10.00 gas card, or shuttle/taxi services for transportation costs.

## **Data Collection**

*Self-reported data.* Baseline assessment for WELL participants will take place within the 4 weeks that precede the start of the CDSMP classes. Post-intervention assessments will be scheduled at 6-, 12- and 18-month after baseline. All patient-reported measures will be collected online using the RedCap database. WELL participants will have a 2-week window to respond to the online surveys. Participants without computer access or those who do not complete the online survey within 2 weeks will be phone-interviewed.

All self-reported measures collected for WELL participants are included in the GOAL survey and summarized in Table 1. The time needed to complete the self-reported data survey will be between 20 and 40 minutes.

*Data on Health Service Utilization (HSU).* These data will be obtained by a well-established linkage procedure that links the GOAL cohort data with the GA Hospital Discharge Database (IRB#55041). This database contains claims data on emergency department (ED) visits and hospital admissions, including causes of admissions and ED visits.

## **CDSMP Implementation**

The CDSMP consists of six weekly sessions, each lasting 2.5 hours, led by two peer leaders and conducted in a small group workshop format with 10 -16 participants. CDSMP clients are community adult men and women of all races and ages with a variety of chronic conditions (e.g., diabetes, heart disease, arthritis) who all are interested in learning self-management skills. WELL participants will be referred to CDSMP at community centers in Atlanta. Participants will have the flexibility to register for workshops based on the convenience of the location and CDSMP schedule. The importance of attending all CDSMP classes will be emphasized during recruitment. Attendance at 4 or more classes will be considered “program completion” for purposes of analyses. The PC will check in with each participant about the last week’s class attendance at the reminder phone call for the next class. Reasons for missing classes will be collected.

**CDSMP Certified Leaders:** CDSMP lay leaders are trained and certified according to the Stanford Patient Education Center Protocol, updated in 2012. Leaders will be selected and overseen by the community organizations offering the classes and will not receive any specific training from the research team on SLE.

## **Analytic Methods**

Data will be organized and cleaned following quality control procedures after each wave, involving identifying outliers and inappropriate patterns of missing data. Psychometric properties of known measures will be compared with reported properties. For multi-item scales and indices, we will use methods such as reliability and factor analyses for data reduction and formation of composite summary variables. Confirmatory factor analyses will be conducted to evaluate the consistency and fit of individual items to a combined construct. We will make every attempt to avoid missing data by discouraging omissions, e.g., by ensuring confidentiality of responses in the

study description and encouraging participants to respond to each question.

For patient-reported and health services utilization outcomes, analysis of repeated measures data is needed that properly accounts for the correlation between multiple observations from the same participant. Two commonly used models to analyze such data will be employed: the mixed-effects model and the generalized estimating equations (GEE) approach. Both approaches allow for covariate adjustment. The results will be summarized with adjusted means and 95% confidence intervals for continuous outcomes. GEE can also be used to analyze count data (e.g., ED visits), ordinal data, and to perform a logistic regression of repeated binary responses within participants. Low classes attendance may attenuate outcome change and have a negative impact on study integrity. Longitudinal analyses will allow us to estimate the effect of CDSMP attendance (# of classes attended) on outcome change.

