### **SOURCES OF MATERIALS**

Involvement of human subjects for this study includes the completion of surveys, participation in the Chronic Disease Self-Management Program (CDSMP) and optional semi-structured interviews among those participants enrolled into the WELL cohort. Surveys will be done at four intervals (baseline, 6-month, 12-month, and 18-month post baseline) by computer or by telephone. WELL participants will attend the CDSMP workshop at a convenient location. Through quota-sampling, a purposive sample of 25 CDSMP participants will be enrolled in a qualitative substudy to participate in semi-structured interviews. Interviews will be conducted in-person at two intervals (pre- and post- CDSMP workshop completion).

As previously discussed, the types of data that will be obtained from WELL (CDSMP) participants are self-reported data from questionnaires and semi-structured interviews. Validated instruments will be used to examine self-management behaviors and health-related quality of life. NIH-PROMIS measures will be used to assess the specific health-related quality of life domains. Self-administered data will be collected

through online surveys using the Research Electronic Data Capture (REDCap), which is a mature, HIPPA compliant secure web application for building and managing online surveys and databases. Participants may also request to have the questionnaire interviewer-administered via telephone.

Qualitative semi-structured interviews will be designed to explore personal definitions of successful self-management, health-related quality of life, health service utilization and challenges to the successful management of SLE. Interviews will be audio recorded and transcribed verbatim. Audio recordings and transcripts will be stored on an encrypted password-protected computer. Any printed transcripts will be stored in locked cabinets.

De-identified data routinely collected from those GOAL participants receiving usual care, who meet the same inclusion and exclusion criteria than WELL participants (CDSMP group), will be used to enable the comparison of study outcomes between the CDSMP group and the usual care group.

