Health services utilization data will be obtained under the auspices of the Georgia Department of Public through a well-established procedure that links the GOAL cohort data with the GA Hospital Discharge Database. Thus, for both the CDSMP and usual care groups, administrative claims data regarding emergency department visits and hospitalizations will be captured from the GA Hospital Discharge Database. This includes the number and characteristics of visits to the emergency department and the number and characteristics of hospital admissions. These data will be stored on an encrypted password-protected computer. Emory University and GA Department of Public Health have provided the IRB approval needed to conduct the databases linkage necessary to obtain health services utilization data for the GOAL population-based cohort.

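### ED visits and admissions are to be compared between WELL and usual care with no matching time zero for usual care and no person-time rule for either group; an added analysis from the date of the draw would give both a common start

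*Combined protocol and SAP*

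**What the plan says.** Reducing health care use is part of the study purpose (Background), and Table 1 lists ED visits and hospitalizations among the study measures. On source and comparison, the plan says:

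- Data Collection describes a procedure that "links the GOAL cohort data with the GA Hospital Discharge Database".
- Sources of Materials adds that "for both the CDSMP and usual care groups, administrative claims data regarding emergency department visits and hospitalizations will be captured", and describes the content: "This includes the number and characteristics of visits to the emergency department and the number and characteristics of hospital admissions".
- The same section says that GOAL data on women in usual care "will be used to enable the comparison of study outcomes between the CDSMP group and the usual care group".

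On analysis, Analytic Methods says "For patient-reported and health services utilization outcomes, analysis of repeated measures data is needed" and names the mixed-effects model and GEE. On counts it says only that "GEE can also be used to analyze count data (e.g., ED visits), ordinal data".

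On timing, Data Collection says, under self-reported data, that "Baseline assessment for WELL participants will take place within the 4 weeks that precede the start of the CDSMP classes" and that "Post-intervention assessments will be scheduled at 6-, 12- and 18-month after baseline". Design Overview and the ClinicalTrials.gov section give the same four time points for the study's measures in general. Both say that the usual-care group is made up of GOAL women not selected for the intervention and that these women continue annual GOAL assessments.

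**The concern.** A count compared between groups over time needs, for each woman, a start date, a period and time at risk. The plan does not give these on a common basis, and the start date it implies for WELL has no counterpart in usual care.

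The way the groups are formed makes this matter more. The random draw makes women drawn comparable with women not drawn. The planned comparison instead sets women who were drawn, agreed, registered and reached a baseline shortly before class against women who were never drawn. Reaching that baseline can depend on health: Recruitment and Informed Consent gives illness and hospitalization among the reasons for rescheduling. Health also drives ED visits and admissions. What is at stake is whether a difference in utilisation, which is a stated aim, can be attributed to the programme.

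**Working it through.** The plan gives no event rate, power statement or utilisation figure, so there is nothing to reproduce. The check sets the sections side by side and then uses simple arithmetic.

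**1. What each group has for linked events.**

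| Element | WELL | Usual care |
|---|---|---|
| Start date | Inferable: baseline, up to 4 weeks before class | None |
| Interval | Inferable: 6 months | Annual GOAL assessments, not tied to any WELL date |
| End or censoring rule | None | None |
| Person-time or offset | None | None |

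The WELL entries come from Design Overview and the ClinicalTrials.gov section read with Table 1. Data Collection places these times under self-reported data and does not carry them over to the linked records.

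**2. Whether rescheduling can move the WELL date.** The order of events is draw, telephone contact and consent, class registration, baseline (within 4 weeks before class), class. There are two cases.

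- A woman postpones after a baseline is recorded. Keeping the first recorded date protects against this.
- A woman postpones for illness before any baseline is taken. Her only baseline then falls after the illness. Nothing is retaken, and a rule to keep the first date does not help.

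Only the date of the draw precedes both cases.

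**3. Who is compared.** Under Design Overview, WELL women are the enrolled part of those drawn, and usual care is those not drawn. Women drawn but not enrolled are in neither group. The draw protects the contrast of all drawn with not drawn. It does not protect the contrast of enrolled with not drawn.

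**4. Why windows must match (illustration only).** Let both groups have the same yearly rate r. A 6-month count in WELL averages 0.5r and a 12-month count in usual care averages r.

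- Without an offset: 0.5r / r = 6/12 = 0.50.
- With person-time: (0.5r / 0.5) / (r / 1) = 1.00.

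**5. What an analysis of all women drawn would cost in dilution.** Let e be the share of drawn women who enrol, w the months from draw to class, and T the months of follow-up. Assume a true ratio of 0.80 from class start in every enrolled woman, no effect in the others, and the same underlying rate in both. Then:

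observed ratio = 1 - e × 0.20 × (T - w)/T

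| Assumed e, w | T = 12 | T = 18 |
|---|---|---|
| 0.70, 2 months | 1 - 0.14 × 10/12 = 0.883 | 1 - 0.14 × 16/18 = 0.876 |
| 0.30, 6 months | 1 - 0.06 × 6/12 = 0.970 | 1 - 0.06 × 12/18 = 0.960 |

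For contrast, take the enrolled comparison in women not rescheduled, with at most 4 weeks between baseline and class. It would show at most (4 + 48 × 0.80)/52 = 0.815 at 12 months and (4 + 74 × 0.80)/78 = 0.810 at 18. It is less diluted, but it is the comparison open to selection.

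**The case against.** **WELL does have a clock.** The general statement of time points in Design Overview, with ED visits and hospitalizations in Table 1 and a repeated-measures analysis, lets a reader infer WELL's origin and intervals. This stands. A reader might infer that neither group has any time frame, and that goes too far. The gap is the usual-care date and, in both groups, person-time and censoring.

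**Offset and equal windows are routine.** A competent analyst would add them, and dated records can be cut at any interval. This also stands. A reader might take the 0.50 above as an error in the plan, but nowhere does the plan say that counts will be cut at 6 and 12 months. An offset, however, does not choose a start date for usual care, and it does not correct for who reaches a baseline.

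**Rescheduling.** A reader might infer that postponement for illness lowers WELL's rate. The documents do not support a direction or a size. They do not say how many women were affected, at what stage, or how their later event rates would compare. The 18 added places (168 - 150) cover workshop cancellations as well as personal reasons and are not a count of postponements for illness. The opposite inference, that keeping the first baseline removes the problem, fails on the second case in step 2.

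**Women who decline.** Sources of Materials describes the comparators as GOAL participants receiving usual care, which could be read to include women drawn who declined. The plan does not say so, and that reading would bring selection into both groups.

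**Unseen sources.** The linkage runs under a separate approval, and the plan commits to registration. Either might fix dates. That the choice is still open can be said of this document only.

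**Conclusion.** The point holds as an omission with a practical remedy. Usual care has no date corresponding to the WELL baseline, neither group has a person-time or censoring rule, and the planned groups leave out women drawn but not enrolled. A comparison of enrolled WELL women from their baseline with non-selected women therefore has no common time zero and is open to selection.

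No bias can be sized or signed from the documents. The 0.50 is an illustration. The dilution range of about 0.88 to 0.97 at 12 months describes the remedy, and every input to it is assumed. The conclusion rests on the text of the plan and needs none of these figures. The change should be made, as a cheap improvement. It is not a ground for holding the study.

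**What to change.** Before the linked data are analysed, state the following.

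1. **All women drawn against women not drawn.** Add an analysis of linked utilisation that includes every woman drawn, enrolled or not, and compares her with women not drawn who meet the same criteria as far as GOAL records allow. Judge those criteria in both groups from the same records. Count from the date of the draw, by wave if the draw was staged, and say how a woman drawn in a later wave is handled. This is the index date that rescheduling cannot move.
2. **The enrolled comparison beside it.** Use the first recorded WELL baseline and assign the same calendar dates to eligible usual-care women. State that it still carries selection at enrolment and from illness-related postponement before baseline.
3. **Time at risk.** Use the same fixed windows in both groups, for example 0-6, 6-12 and 12-18 months, with log person-time as offset. End follow-up at death, at the end of the linked data or, where GOAL records it, at a move out of Georgia. Where moves are not recorded, state this as a limitation, because care outside the state would not appear in a Georgia database.

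The cost is analysis wording, a dated list of the draw, and date cuts in a linkage that Sources of Materials describes as already approved for the GOAL cohort. The sponsor should confirm that the approval covers this use. No new participant contact is needed. The downside is the dilution shown above, from women who never attend and from time before class, so the two analyses should be reported together with the weakness of each stated.

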## **Design Overview**

A random sample selected from our GOAL cohort will be used to recruit AA women with SLE into the WELL (Women Empowered to Live with Lupus) cohort. WELL participants will attend the CDSMP classes in the community, along with people with other chronic illnesses. Measures will be completed at baseline, 6, 12, and 18 months. AA women from the GOAL cohort non-selected to be assigned to the intervention will comprise the usual care group. They will continue their routine annual assessments as part of the GOAL cohort efforts.

We will also conduct a longitudinal qualitative substudy to learn about African American women's perspectives on (a) the processes through which the CDSMP affects self-management behaviors, health-related quality of life (HQRL), and healthcare service use; and (b) identify remaining challenges to successful SLE self-management after CDSMP participation.

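### CDSMP is delivered in led workshops, but the analysis commits only to within-participant correlation; if shared delivery makes women's outcomes alike, CDSMP versus usual-care standard errors are too small, by an amount the documents cannot fix

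*Combined protocol and SAP*

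**What the plan says.** CDSMP Implementation describes six weekly sessions, "led by two peer leaders and conducted in a small group workshop format" with 10 to 16 people. Those people are community clients with various chronic conditions, so WELL women are only some of them. On how women reach a class, the same section says: "Participants will have the flexibility to register for workshops based on the convenience of the location and CDSMP schedule".

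The comparator has no such structure. Design Overview says "AA women from the GOAL cohort non-selected to be assigned to the intervention will comprise the usual care group", and of those women, "They will continue their routine annual assessments as part of the GOAL cohort efforts". Sources of Materials confirms that outcomes will be compared between the two groups.

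Analytic Methods is the only quantitative analysis text. Its statement on dependence is that "analysis of repeated measures data is needed that properly accounts for the correlation between multiple observations from the same participant". It names mixed-effects models and GEE, with covariate adjustment and the number of classes attended. That number, like the four-class completion rule, measures dose; it is not a cluster term. Nowhere is workshop, leader or site named as a random effect, a GEE cluster or a sensitivity analysis.

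Two further statements matter for the mechanism. On timing, Data Collection says "Baseline assessment for WELL participants will take place within the 4 weeks that precede the start of the CDSMP classes". On sampling, Recruitment and Informed Consent says "Each woman will have the same probability of being chosen at any stage of the sampling process".

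**The concern.** A participant random effect, or GEE clustered on participant, treats different women as independent. If leaders or group dynamics move the women of one workshop together, the CDSMP arm carries variance that those standard errors omit. Under no true effect, intervals would then exclude zero more often than 5% of the time, about equally in each direction.

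Two sources of likeness have to be kept apart:

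- **Sorting.** Women in one workshop may be alike because they chose the same place and time. This alone does not inflate error, because women are sampled individually and grouped only afterwards.
- **Delivery.** Women may become alike because they shared leaders and a group. This does inflate error. It can act only after baseline, because baseline is measured before the classes.

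**Working it through.** The documents give no power, effect size or standard deviation, so there is no figure of the plan's to reproduce.

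**Inputs**

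- WELL women: 168 (Recruitment and Informed Consent: "Enrollment number increased to 168 to accommodate participants on a waiting list due to workshop cancellations"). All are taken as analysed, which is an assumption.
- Usual-care women, nC: not stated; 168 and 400 assumed.
- WELL women per workshop, m: not stated; 2 to 5 assumed, with 10 as a larger case.
- ICC, the workshop share of variance in the outcome as compared (change or baseline-adjusted): not stated; 0.01 to 0.05 assumed, with 0.10 as a high case.
- Error level: two-sided 5%, read from the 95% intervals.

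**Formulas** (clustering in one arm, all likeness due to delivery)

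- DE = 1 + (m − 1) × ICC
- R = (DE/168 + 1/nC) / (1/168 + 1/nC)
- Standard error understated by 1 − 1/√R
- Type I error = 2 × (1 − Φ(1.96/√R))

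**Worked case,** m = 5, ICC = 0.05: DE = 1 + 4 × 0.05 = 1.20.

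- nC = 168: R = (1.20 + 1)/2 = 1.100 and √R = 1.049. The standard error is 4.7% too small and type I error is 6.2%.
- nC = 400: R = (0.007143 + 0.0025)/(0.005952 + 0.0025) = 1.141 and √R = 1.068. The standard error is 6.4% too small and type I error is 6.7%.

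| m | ICC | DE | R (nC 168 / 400) | SE too small by | Type I error |
|---|---|---|---|---|---|
| 1 | any | 1.00 | 1 / 1 | 0% | 5.0% |
| 2 | 0.01 | 1.01 | 1.005 / 1.007 | 0.2% / 0.4% | 5.1% / 5.1% |
| 5 | 0.05 | 1.20 | 1.100 / 1.141 | 4.7% / 6.4% | 6.2% / 6.7% |
| 5 | 0.10 | 1.40 | 1.200 / 1.282 | 8.7% / 11.7% | 7.4% / 8.3% |
| 10 | 0.05 | 1.45 | 1.225 / 1.317 | 9.7% / 12.9% | 7.7% / 8.8% |

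If only half of the likeness is delivery, m = 5 with an observed ICC of 0.05 gives 2.4% to 3.3% and 5.6% to 5.8%. For a given observed ICC, the table is therefore an upper bound.

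**Simulation of the two mechanisms.** There were 24,000 null trials per setting, with a baseline-adjusted outcome, an assumed baseline correlation of 0.6, 84 workshops of 2 or 34 of 5, nC 168 or 400, and ICC 0.01 or 0.05.

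- Delivery: type I error 5.1% to 6.5% without workshop clustering, 5.0% to 5.3% with it.
- Sorting with the same observed ICC: 4.8% to 5.3% without clustering, 3.5% to 5.2% with it.

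**Which workshop term works.** Take two visits with correlation 0.6 and unit variance, so a woman's change has variance 2 × (1 − 0.6) = 0.8. Add a post-baseline workshop variance of 0.05 in the CDSMP arm, with m = 5 and nC = 168.

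- True standard error: √[(0.8 + 0.05 + 4 × 0.05)/168 + 0.8/168] = 0.1049.
- Workshop variance left out altogether: √(0.8/168 + 0.8/168) = 0.0976. A time-constant workshop intercept also gives 0.0976, because it cancels from the change.
- Participant variances right but sharing ignored: √[(0.8 + 0.05)/168 + 0.8/168] = 0.0991. Ignoring the sharing costs 1 − 0.0991/0.1049 = 5.5%.

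Where baseline is one of the repeated outcomes, a plain workshop intercept therefore does not cure the problem.

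All of this is for a continuous outcome. ED visits and hospitalizations, as counts, were not calculated.

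**The case against.** The strongest reply has four parts.

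1. **Silence is not exclusion.** Analytic Methods explains why repeated-measures methods are needed; it does not list every random effect, and both model classes could include a workshop level. This stands as far as it goes: a reader might infer that the plan rules out workshop clustering, and it does not. But it commits to nothing beyond the participant, and the analysis cannot be done without a workshop code in the analytic file.

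2. **The size is assumed.** This stands. WELL women per workshop could be 1, and the only route into a workshop that the documents describe is self-selection. A reader might go the other way and use the 10 to 16 attendees as the cluster size: m = 16 with ICC 0.05 gives type I error of 9.2% to 12.0% for 150 to 600 usual-care women. The documents do not support that, because classes are mixed with other clients. A four-visit calculation with workshop variance 0.10 gives a standard error of 0.0797 against a true 0.0966, which is 17.5% too small (type I error about 10.6%). It assumes four visits in both arms, whereas usual-care women are assessed annually.

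3. **The cure can cost about as much as the problem.** This stands in part. Under pure sorting, clustering took simulated type I error down to 3.5%, about as far below 5% as the core range goes above it. That argues for reporting both analyses, not for omitting the clustered one.

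4. **The data will not show which mechanism holds.** This stands. The large-sample standard error of an ICC of 0.05 is about 0.063 with 34 workshops of 5 and 0.109 with 84 of 2; F-test power is about 23% and 12%. Comparing baseline with post-baseline ICCs would be weaker still.

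**Conclusion.** The concern holds in conditional form. As written, the plan makes no provision for correlation between WELL women taught in the same workshop. If at least two share a workshop and delivery makes their post-baseline outcomes alike, the standard errors for CDSMP versus usual care are too small.

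The likely size depends on m, the ICC and the usual-care number, none of which the documents state. In the core range it is modest; with about 10 WELL women per workshop and ICC 0.05 it would be larger, at 7.7% to 8.8% type I error.

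A reader might infer that the comparison is invalid or its estimate biased. Neither follows: the issue affects precision and error rate only. Priority is minor to moderate.

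**What to change.** 1. Carry a de-identified code for the workshop actually attended into the analytic file under the study ID. The attended workshop is the one that matters, because women may be rescheduled.
2. Pre-specify a partially nested analysis of CDSMP versus usual care, reported beside the participant-only analysis. In the mixed model, add to the participant effect a workshop effect in the CDSMP arm that acts after baseline: a workshop random intercept if baseline is a covariate, or a workshop-by-post-baseline random effect if baseline is a repeated outcome. State which is used. Alternatively, use GEE clustered on workshop with a small-sample variance correction. In either case, usual-care women and CDSMP women who attended no class are their own clusters.
3. Report the number of WELL women per workshop and the workshop ICC with its confidence interval. Do not use baseline versus post-baseline ICCs to decide between sorting and delivery.

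**Cost.** A few sentences in Analytic Methods and minor data handling. The coordinator already handles registration and attendance, but Protections Against Risks keeps CDSMP tracking in a separate secure database, so the link by study ID has to be planned. The clustered intervals will be slightly wider, somewhat conservative if the likeness is mainly self-sorting, and based on an imprecisely estimated workshop variance.

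### Number of classes attended is self-selected, so the planned attendance analysis gives an association, not an effect, and its false slope can go either way

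*Combined protocol and SAP*

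**What the plan says.** Analytic Methods names mixed-effects models and GEE, chosen because they account for repeated observations on the same woman. It warns that low attendance may dilute outcome change and then states: "Longitudinal analyses will allow us to estimate the effect of CDSMP attendance (# of classes attended) on outcome change". On confounders it says only "Both approaches allow for covariate adjustment". It names no covariate and does not say whether the baseline outcome is a response or a covariate.

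The random step is earlier. Design Overview: "A random sample selected from our GOAL cohort will be used to recruit AA women with SLE into the WELL", and "AA women from the GOAL cohort non-selected to be assigned to the intervention will comprise the usual care group". Recruitment and Informed Consent makes clear that the draw is for an offer.

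CDSMP Implementation gives the exposure: "The CDSMP consists of six weekly sessions". Attendance is encouraged but not assigned, and women choose workshops by convenience. "Attendance at 4 or more classes will be considered" completion for analysis. "Reasons for missing classes will be collected", with no analytic use stated. Under Data Collection, "Post-intervention assessments will be scheduled at 6-, 12- and 18-month after baseline".

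Table 1 groups disease activity, organ damage, multimorbidity and depression as severity measures. The section on data accuracy mentions covariate data. Neither is assigned to the attendance analysis.

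**The concern.** The sentence makes a causal claim about an exposure that each woman sets for herself after the random step. Modelling within-woman correlation does not make women who attend six classes comparable with women who attend two. The completion flag has the same weakness.

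What is at stake is how a dose-response slope would be read. A rising slope looks like support for CDSMP, and a flat or falling one looks like evidence against it. With no programme effect at all, three mechanisms give different false pictures:

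- **(a) Illness during the course** lowers attendance and worsens later outcome. The slope is falsely favourable with or without baseline adjustment.
- **(b) Attendance follows the observed baseline score.** If better-scoring women attend more, raw change shows false harm through regression to the mean. Baseline adjustment removes it.
- **(c) Attendance follows stable severity.** Raw change is unbiased. Entering baseline as a covariate creates a false benefit, because one noisy score does not capture severity.

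If sicker women attend more, the signs reverse. The documents do not show which mechanism operates, so no single adjustment is known to be safe.

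**Working it through.** **No figure to reproduce.** The documents give no significance level, outcome SD, expected attendance or expected slope.

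**Inputs from the documents:** n = 168 (enrolment raised from 150) and six classes.

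**Assumed:** analysis within the intervention cohort; no programme effect; no missing data; two-sided 5% test; outcome SD 1, higher is better; correlation between waves r = 0.7; 6-month change as outcome; classes ~ Binomial(6, expit(1.0 − k·s)), where s is the driver of attendance (the severity or illness score).

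**Step 1, strength of selection.** Let ρ be the size of the correlation between classes and s. With p = expit(1.0) = 0.731 and v = 6p(1−p) = 1.18, approximately ρ = vk/√(v + v²k²). For k = 0.8 this is 0.944/√(1.18 + 0.891) = 0.66. Simulation gives 0.64, with mean 4.24 classes, SD 1.386 and 72% attending four or more. For k = 0.4, 0.25 and 0.1 the formula gives 0.40, 0.26 and 0.11 (simulated 0.39, 0.26, 0.11).

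**Step 2, false slope per class at ρ = 0.64.**
- (a) Illness correlated b = 0.2 with worse change: b√(2(1−r))·ρ/SD = 0.2 × 0.775 × 0.64/1.386 = +0.07.
- (b) Raw change: −(1−r)ρ/SD = −0.3 × 0.64/1.386 = −0.14.
- (c) Baseline-adjusted: √r(1−r)ρ/[SD(1−rρ²)] = 0.837 × 0.3 × 0.64/(1.386 × 0.713) = +0.16.

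Simulated slopes are 0.071, −0.138 and 0.161.

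**Step 3, chance of false significance.** Let R be the size of the (partial) correlation between classes and change, and δ = √168·R/√(1−R²). The rate is about Φ(δ−1.96) + Φ(−δ−1.96).
- (a) R = bρ/√(1+b²) = 0.196ρ.
- (b) R = ρ√((1−r)/2) = 0.387ρ.
- (c) R = √r(1−r)ρ/√((1−rρ²)(1−r²)).

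Example, (b) at ρ = 0.64: R = 0.248, δ = 12.96 × 0.248/0.969 = 3.32, rate = Φ(1.36) = 91%.

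| ρ | (a) raw change: formula / simulated | (b) raw change: formula / simulated | (c) baseline-adjusted: formula / simulated |
|---|---|---|---|
| 0.64 | 37% / 36% | 91% / 91% | 95% / 93% |
| 0.39 | 17% / 17% | 51% / 50% | 48% / 48% |
| 0.26 | 10% / 10% | 26% / 25% | 23% / 23% |
| 0.11 | 6% / 6% | 9% / 8% | 8% / 8% |

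**Step 4, the other estimator in each case.** In (a), baseline adjustment leaves the bias: about 41% at ρ = 0.64, against 36% raw. In (b), adjustment brings the rate to about 5%. In (c), raw change stays at about 5%.

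**Step 5, a second set of assumptions.** A separate simulation used a different attendance distribution (mean about 3.9, SD about 1.8), the mean of the three follow-up waves, and r = 0.5 and 0.7. It gave the same pattern. With a correlation of about 0.10 to 0.28 between attendance and baseline, the biased estimator in (b) or (c) was significant in 14% to 59% of trials. Mixed-model and GEE fits, checked at r = 0.5, agreed with the simple slopes to within about 0.01.

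**The case against.** The strongest reply is that this is a secondary matter inflated by assumption. Much of it stands.

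- **Role of the analysis.** It is not labelled primary, it is introduced to address dilution from low attendance, and no text says it will support efficacy. No analysis using the completion flag is described. This limits the seriousness of the point but does not justify a causal word with no caveat.
- **Strength of selection.** Rates above 90% need a correlation of about 0.64, which nothing in the documents supports. At 0.11 the rates are 6% to 8%, close to nominal. The range has to be shown.
- **Case (c).** It arises only if baseline is a covariate. Analytic Methods leaves this open, and an attendance-by-time model with baseline as a response behaves like raw change.
- **Health as the driver.** That health affects attendance is an inference. The recruitment section links illness and hospitalization only to rescheduling.
- **Severity data exist.** Table 1 measures could be used, but imperfect ones help only in part: in (c) at ρ = 0.64, adding two half-reliable severity measures still leaves 68%.

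A reader might infer that the comparison with usual care is compromised, or that a false attendance finding is likely in this trial. The documents support neither. That comparison does not use classes attended, and the size and sign of any bias cannot be found from the plan.

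**Conclusion.** The point holds for the attendance analysis and for any completer analysis. The plan claims an effect where its design yields an association, and nothing in the text handles the confounding. This conclusion needs no simulation. The size is illustrative: depending on mechanism and strength of selection, false significance runs from roughly the nominal 5% to above 90%, with either sign. Those rates assume r = 0.7, a 5% test, the attendance model above and, for (a), an illness correlation of 0.2. Baseline adjustment is neither a general cure nor a general error: it helps in (b), harms in (c) and does nothing useful in (a). The correction is worth making because it is cheap and changes what may be concluded from the slope.

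**What to change.** **Wording.** In Analytic Methods, replace the sentence by: *Exploratory longitudinal analyses will describe the association between the number of CDSMP classes attended and outcome change; they will not be used as evidence for or against CDSMP efficacy.* Give any completer analysis the same label.

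**Model.** Prespecify how baseline enters. Preferably report two analyses side by side: unadjusted change, and one adjusted for the baseline outcome and the Table 1 severity measures. Disagreement suggests confounding. Agreement is not proof of its absence, since in (a) both err in the same direction. Report reasons for missed classes descriptively.

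**Cost.** A weaker attendance statement and one extra model on data already collected.

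**Optional, only if a causal per-class estimate is wanted.** Use the random draw as an instrument, mainly for the claims-based ED visits and admissions linked for the whole GOAL cohort. The plan would have to:
- keep drawn women who decline in the drawn group with 0 classes;
- define a common time zero, since baseline is tied to class start and other women have no such date;
- apply eligibility in the same way to drawn and non-drawn women;
- state that the offer acts only through the classes, noting that payments, transport, reminder calls and interviews are possible other routes.

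Simulated error rates of 4.6% to 5.2% for this approach hold only under those assumptions. Precision depends on uptake u, which the documents do not give. With 168/u drawn, an assumed 200 non-drawn and 4.243 classes per participant, the SE per class is √(u/168 + 1/200)/(4.243u), in SDs of raw change. This is 0.029, 0.042 and 0.065 at u = 80%, 50% and 30%, against 1/(√168 × 1.386) = 0.056 for the within-cohort slope.
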